### 812 G2 Interim Monitoring and Early Stopping

813 There will not be a planned interim monitoring, nor will there be early stopping rules.

### 814 G3 Statistical Methods

815 An intention-to-treat analysis will be used for the primary analysis of the data. All

816 participants will be examined in the groups to which they were initially assigned.

817 Standard descriptive statistics will be used to assess the demographics, clinical

818 characteristics, and olfactory test results of the study population. The difference in rate of

responders after Fixed-Dose period will estimate the effect size of the primary outcome

820 measure, and the 95% CI around that point estimate will measure precision. In each

group, the frequency and relative frequency of the participants' response to the global

rating of smell change will be reported for each Likert category. Fisher's exact test will

be used for comparing the responders' rates between the 2 groups. Histograms and

- 824 Shapiro-Wilks test will be used to test the normal distribution assumption of the
- 825 continuously measured UPSIT scores and the differences pre-post treatment in each of
- the groups. Independent samples t-test or its nonparametric equivalent Mann-Whitney U
- test will be used to compare the change in UPSIT scores between the two groups. Mixed
- 828 effects model will be used to test whether the change in UPSIT score from baseline to
- end of treatment is significantly different between 2 groups. Subjects will be treated asrandom factors, and group and time will be used as fixed factors in the model. Interaction
- of group by time will be explored. Effect sizes with 95% CIs will be reported for each
- analysis. All statistical analyses will be conducted in SPSS 28 (IBM Corp., Armonk,
- 833

NY).

834

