### 794 G1 Sample Size Determination and Power

795 To date there have been no studies investigating efficacy of gabapentin in COVID-19 796 related olfactory dysfunction. Due to the lack of preliminary data and effect size, 797 estimates of the sample size for this study will be determined based on feasibility. For 798 this pilot study, we plan to enroll 60 subjects. The sample size of 60 subjects is feasible 799 given the incidence of COVID-19 cases in Missouri and considering a conservative 800 estimate of a 10% rate of permanent olfactory dysfunction among those (~50%) who 801 experience olfactory dysfunction as one of the presenting symptoms. Using a 33% drop 802 out rate, we estimate that the sample size of 60 subjects randomized in a balanced way 803 between the two treatment groups will provide us with 40 evaluable cases. A previous 804 study exploring a different treatment for COVID-19 related anosmia in our lab showed 805 that 30% of the participants randomized to placebo reported improvement at the end of 806 the trial as compared to baseline. We aim to observe a 25% difference in the response 807 rate between gabapentin and placebo groups. Assuming that this will be the response rate 808 in the placebo group of our trial, the sample size of 20 subjects per group will provide us 809 with a 95% Confidence Interval -5% to 55% around the desired proportion difference of 810 25% between gabapentin and placebo groups.

811

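### Does the primary analysis need a named confidence interval method, and a rule for when the interval and Fisher's exact test disagree?

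*Combined protocol and SAP*

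**What the plan says.** Section G3 (Statistical Methods) gives the primary outcome three outputs. The difference in the rate of "responders after Fixed-Dose period will estimate the effect size of the primary outcome" measure is the estimate. Its "95% CI around that point estimate will measure precision". Fisher's exact test will "be used for comparing the responders' rates between the 2 groups". G3 adds a general commitment, "Effect sizes with 95% CIs will be reported for each" analysis, and on software it states "All statistical analyses will be conducted in SPSS 28". It gives no interval method, no significance level and no sidedness, and it does not rank the interval against the test.

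Section G1 (Sample Size Determination and Power) sets the size by feasibility. Sixty participants randomised "between the two treatment groups will provide us with 40 evaluable cases", and 20 per group are said to provide the trial "with a 95% Confidence Interval -5% to 55% around the desired proportion difference of" 25% between the arms, with placebo response taken as 30%. G1 also leaves the method of that interval unnamed. Section G2 rules out interim monitoring and early stopping rules. No section states a criterion for declaring efficacy.

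**The concern.** Fisher's exact test is conservative in small samples and the simple Wald interval is liberal, so the same 2x2 table can give an interval that excludes zero beside a p-value above 0.05. A score-type interval reduces this but does not remove it, because Fisher's conservatism remains. With the method unnamed, the interval could in principle be picked after the data are seen, and a reader could cite whichever result suits. Sections D3 and 2.e say the pilot results will be used to start a larger trial, so an ambiguous primary result could carry weight there.

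**Working it through.** **Inputs.** From G1: placebo response 30%, difference 25 points (so 55% on gabapentin), 60 enrolled, 33% dropout, 20 evaluable per group. From G3: 95% confidence level and Fisher's exact test. Assumed: two-sided 0.05 for Fisher's test, to match the 95% interval, since the plan states no significance level.

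**The plan's own figures.** Evaluable number: 60 x (1 - 0.33) = 40.2, in line with the stated 40. Wald interval, d ± 1.96 x sqrt[p1(1-p1)/n + p2(1-p2)/n]:

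- variance = 0.55 x 0.45/20 + 0.30 x 0.70/20 = 0.012375 + 0.0105 = 0.022875
- standard error = 0.1512
- interval = 0.25 ± 0.296, or -4.6% to 54.6%

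This rounds to G1's -5% to 55%. For the same 11/20 against 6/20, Newcombe gives -5.2% to 49.6%, Agresti-Caffo -5.8% to 51.2% and continuity-corrected Wald -9.6% to 59.6%. Only plain Wald matches both limits, so G1's figure is correct. It is a planning figure and does not bind the analysis to Wald.

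**Individual tables at 20 per arm (gabapentin against placebo).**

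| Responders | Wald 95% CI | Newcombe 95% CI | Fisher p |
|---|---|---|---|
| 11 vs 6 | -4.6% to 54.6% | -5.2% to 49.6% | 0.200 |
| 12 vs 6 | 0.6% to 59.4% | -0.6% to 53.8% | 0.111 |
| 13 vs 6 | 6.0% to 64.0% | 4.2% to 57.9% | 0.056 |
| 14 vs 6 | 11.6% to 68.4% | 9.0% to 61.9% | 0.026 |

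**How often they disagree.** Every possible table was enumerated and weighted by its exact binomial probability at 55% vs 30%. Disagreement means that the interval excludes zero and Fisher's p exceeds 0.05. The reverse did not occur at any arm size checked.

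| Evaluable (gabapentin/placebo) | Wald | Newcombe |
|---|---|---|
| 20/20 | 19.6% | 10.1% |
| 21/19 | 14.2% | 9.0% |
| 22/18 | 12.4% | 8.7% |
| 18/22 | 10.5% | 8.8% |
| 17/23 | 14.7% | 12.5% |
| 29/27 | 9.6% | 5.0% |
| 30/20 | 6.3% | 4.7% |
| 30/30 | 11.0% | 10.5% |

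If exactly 40 of 30/30 remain and dropout is equally likely in each arm (an assumption), the chance of an exact 20/20 split is C(30,20) x C(30,20) / C(60,40) = 21.5%. The 19.6% is therefore the top of the range checked, not a typical value.

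**How far apart they are.** At 20/20 the largest Fisher p among the conflicts is 0.13 with Wald and 0.096 with Newcombe. About half of the 19.6% (10.1 points) have p between 0.05 and 0.10. With no effect (30% in both arms, 20/20), disagreement is 4.4% for Wald and 2.8% for Newcombe.

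**What replacing the test would do.** At 20/20 and 30% in both arms, the type I error is 2.5% for Fisher and 4.5% for Boschloo's unconditional exact test. At 55% vs 30% the rejection rate is 24.5% for Fisher and 32.5% for Boschloo (40.2% and 49.4% at 30/30). Boschloo and Newcombe still disagree in 2.1% of trials at 20/20 and 1.3% at 30/30.

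**The case for a change.** The strongest case for a change is that the open choice alters the apparent result. At 20/20 and the planned effect, the chance of a seemingly positive finding is 24.5% if Fisher's test is read, 34.6% if a Newcombe interval is read and 44.1% if a Wald interval is read. At 12/20 against 6/20 the interval method alone decides whether zero is excluded. Measuring precision is not the same as saying which result leads, readers do check whether an interval excludes zero, and two sentences of text would settle it.

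The arithmetic stands, and so does the observation that G3 leaves the method unnamed. What does not follow is that the plan yields a wrong answer. The three percentages describe three decision rules, and the plan adopts none of them. The 0.05 threshold is brought in from outside. The interval becomes a second test only if a reader makes it one. Boschloo's gain in rejection rate is also real, but Fisher's test is valid and pre-specified, statisticians differ on conditional versus unconditional tests, no stated power is missed, and the unconditional test may need software beyond the package to which G3 commits all analyses.

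**Conclusion.** The gap is genuine but does not call for a change. G3 already separates the roles: one estimate, one measure of its precision, one test of the comparison. Followed as written, it gives a usable estimate and a valid test. G1 sizes the trial on feasibility and expected interval width, and its own planning interval includes zero, so the design never relied on excluding zero. With no success criterion, a disagreement affects wording only. An interval just above zero beside a p-value between 0.05 and about 0.13 says much the same thing about a pilot: suggestive and imprecise. An analyst would ordinarily name the interval in the report and show both results.

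The size of the issue is about 5-13% of trials with a Newcombe interval and 6-20% with Wald over the arm sizes checked, the upper Wald figure holding only at exactly 20/20. These figures assume two-sided 0.05 and true response rates of 55% and 30%. Substituting an unconditional test is a matter of preference with costs on both sides.

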### 217 **Primary Outcome:**

218 Clinical Global Impression of Improvement Scale (CGI-I). The response rate is 219 defined as the number of participants self-reporting minimal change or larger on 220 the Clinical Global Impression of Improvement Scale (CGI-I) scale, divided by 221 the number of participants in each group. The CGI-Improvement is a self-222 reported scale of improvement ranging from 1 to 7 (1 is Very Much Improved, 7 223 is Very Much Worsened) and will be measured after completing 8 weeks of the 224 fixed, highest-tolerable dose. Each rating is well defined to maximize accuracy. 225 Participants reporting 3 as Minimally Improved, 2 as Much Improved, or 1 as Very 226 Much Improved in the CGI-I will be deemed responders to treatment, and the 227 number of responders to non-responders will be compared between the two arms -228 CGI-Severity (CGI-S) and CGI-Improvement (CGI-I).

229	
230	
231	Secondary Outcomes:
232	1. CGI-Severity. The CGI-Severity scale ranges from 1 to 7, where 1 is normal
233	function and 7 is complete anosmia. This assessment will provide subjective data
234	on patients' baseline olfactory function prior to beginning the trial, after 8-week
235	Fixed-Dose period, and 4 weeks after completion of Taper-Down phase.
236	2. CGI-Improvement. The CGI Improvement will also be administered 4 weeks
237	after completion of Taper-Down phase which same analysis as described above.
238	3. University of Pennsylvania Smell Identification Test (UPSIT).  The UPSIT is
239	composed of 40 strips of microencapsulated odorants, which are present on the
240	bottom of each page, just below a four-alternative multiple-choice question. For a
241	given item, the patient releases an odor by scratching the microencapsulated pad
242	with a pencil tip, smells the pad, and indicates the odor quality from four
243	alternatives. Even if no smell is perceived, a response is required (i.e., the test is
244	forced-choice). The subject's total correct score out of the 40 items is
245	determined. 
246	The total UPSIT score can range from 0 to 40 and scores are interpreted as the
247	level of absolute smell function (i.e., normosmia, mild hyposmia, moderate
248	hyposmia, severe hyposmia, and anosmia), using the age- and sex-related
249	normative classification system described in the UPSIT manual (Table 1) The
250	minimal clinically important difference in UPSIT score is 4.

Disease Classification Based on UPSIT		Women	Men

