### 341 E1 Overview or Design Summary

This study will be a double-blinded, placebo-controlled, randomized pilot clinical trial to evaluate the efficacy of gabapentin to improve post-COVID-19 olfactory dysfunction.

- 344 This study will also describe adverse effects related to oral gabapentin use.
- 345

This study will be conducted via virtual research guidelines and procedures. We will not require in-person patient participation or evaluation. Following initial evaluation to ensure potential participants meet all inclusion criteria and none of the exclusion criteria,

the research study will be explained in full via Zoom call, phone call if necessary.

350 Participants will then be randomized in a 1:1 allocation via permuted-block sequencing

into the oral gabapentin group or the placebo group. All assessments will be conductedthrough a HIPAA-compliant online survey form. Baseline assessments will help us

determine subjective and objective rates of olfactory dysfunction. Assessments will be

354 conducted again after the 8-week Fixed-Dose period and 4 weeks after completing taper.

355 356	The primary objective of this study is to assess the efficacy of oral gabapentin in improving olfactory dysfunction secondary to COVID-19.
357	E2 Subject Selection and Withdrawal
358	
359	2.a Inclusion Criteria
360	Participants will be recruited based on the following inclusion criteria:
361	- Men and women between the ages of 18 and 65 years
362	- Residing within the states of Missouri or Illinois
363	- Clinically diagnosed or subjective olfactory dysfunction (anosmia, hyposmia,
364	or parosmia) of at least 3 months duration associated with COVID-19
365	infection

- 366- initial UPSIT score consistent with diminished olfactory function (score  $\geq 6$ 367and  $\leq 33$  in men and score  $\geq 6$  and  $\leq 34$  in women).
- Willing to respond daily to study surveys, preferably through smartphone with
   unlimited texting plan.
- In possession of all 7 household items associated with *NASAL-7*: soap, burnt
  candle, peanut butter, herb, garlic, lemon, and coffee

373 2.a Exclusion Criteria

Individuals will not be allowed to participate in this study if they meet one or more of thefollowing exclusion criteria:

- Clinically diagnosed olfactory dysfunction secondary to non-COVID-19 viral
   infection, genetic abnormalities or congenital dysfunction, trauma, nasal
   polyps, neurodegenerative disorders
- 379
  380

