  Current use of: azelastine, bromperidol, orophenadrine, oxomemazine, kratom, paraldehyde, or thalidomide
- 381 History of addiction to alcohol, cocaine, or opioids
- 382 Impaired renal function, myasthenia gravis, or myoclonus
- 383 Severe allergy to peanuts
  384 Pregnancy or attempting p
  - Pregnancy or attempting pregnancy during study participation
- Inability to participate in virtual trial due to lack of access to the; inability to
   comprehend or use English language
- 387 Availability less than 18 weeks from time of enrollment
- 388 Residency in states other than Missouri or Illinois.
- 389 **2.b** Ethical Considerations
- This study relies on participation of human subjects. Informed consent will be obtained from each participant to ensure their safety, minimize risk, and ensure full confidentiality. All assessments will be conducted virtually via HIPAA-compliant online surveys at baseline and then throughout the study course. Selection of participants for the study will consider the variability in response to COVID-19 as well as response to gabapentin by ensuring the two groups are matched 1:1 by permuted block randomization. Gabapentin has a slight risk of dependence in individuals with previous

history of alcohol, cocaine, or opioid abuse so these patients will be excluded from the

study.The study team will be available at all times for participants during the full course
 of the trial.

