#### 481 3.c Method for Assigning Subjects to Treatment Groups

482 The participants will be divided using permuted block randomization in a 1:1 allocation

- 483 between two arms: the oral gabapentin group and the oral lactose placebo group with 20
- 484 persons in each group.

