### 523 F1 Screening for Eligibility

524 Individuals who reach out with interest in the study after seeing the approved study flyer or who have contacted RA for participation in similar studies for which recruitment has 525 ended will asked to complete an online screening questionnaire (survey titled: 526 527 "ScreeningSurvey") to ensure he or she meets all the inclusion criteria and does not meet any exclusion criteria. Following eligibility confirmation, the RA will collect information 528 529 required to mail screening smell identification test (UPSIT). Once received, the 530 participant will complete the UPSIT and provide their response virtually through the 531 REDCap survey. Once eligibility is confirmed based on UPSIT score, participants will 532 be provided through REDCap an online consent form to review and complete. The RA 533 will offer each participant the option to review the consent form independently or with the RA via zoom or phone call (zoom as the preferred option). Once the participant 534 535 electronically signs the consent form, the RA will review it and sign. The REDCap 536 software will automatically email the participant a copy of their completed form.

[figure not shown]

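### The UPSIT analyses do not condition on baseline UPSIT; ANCOVA on a score already collected would usually be more precise (one secondary outcome)

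*Combined protocol and SAP*

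**What the plan says.** Section C3 lists UPSIT third among six secondary outcomes. It states "The total UPSIT score can range from 0 to 40" and gives a minimal clinically important difference of 4 points.

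Section G3 plans two between-group comparisons:

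- After a normality check, the t-test or Mann-Whitney U "test will be used to compare the change in UPSIT scores between the two groups".
- A mixed model asks whether change from baseline to end of treatment differs by group. Subject is random, "group and time will be used as fixed factors in the model", and the interaction "of group by time will be explored".

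No baseline covariate is named for either, and ANCOVA appears nowhere in the document.

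A baseline value exists for everyone. The inclusion criteria in E2 require an "initial UPSIT score consistent with diminished olfactory function" (6 to 33 in men, 6 to 34 in women). Under F1, before consent, the "participant will complete the UPSIT and provide their response virtually through the" REDCap survey.

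On allocation, E3 3.c says "The participants will be divided using permuted block randomization in a 1:1 allocation" and names no stratification factor. E2 2.b nevertheless speaks of "ensuring the two groups are matched 1:1 by permuted block randomization".

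**The concern.** A change score uses baseline by subtracting all of it, which fixes the slope of follow-up on baseline at 1. When the true slope is below 1, as it is with equal SDs and imperfect correlation, this over-corrects. The estimate is then noisier than it need be, and in a given trial it leans against whichever group happened to start higher. ANCOVA estimates the slope from the data.

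The mixed model does not fill the gap, because with complete data at two visits it repeats the change-score comparison. Baseline balance is left to chance: permuted blocks equalise group sizes, not baseline scores, so they do not match the groups in any prognostic sense.

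There is also a wording point. The mixed model's stated question is whether change differs between groups. The group-by-time term answers that question, yet G3 only undertakes to explore it.

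At stake is the width of the UPSIT confidence interval and its sensitivity to chance imbalance, with about 20 evaluable participants per group.

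**Working it through.** **The plan's own figure.** G1 gives one precision statement, for the CGI-I responder difference (30% vs 55%, 20 per group): 0.25 ± 1.96 × √(0.30×0.70/20 + 0.55×0.45/20) = 0.25 ± 0.296, or -4.6% to 54.6%. This matches the stated -5% to 55%. It does not concern UPSIT, for which the plan gives no precision.

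**Inputs.** From the documents: 20 evaluable per group (G1) and the eligibility range. Assumed, because the documents are silent: baseline SD s of 5 to 8 points, baseline/follow-up correlation r of 0.5 to 0.8, and follow-up SD of k × s with k = 1 or 1.25. For scale, an even spread of integer scores over 6–33 or 6–34 has SD 8.1 or 8.4. The case k = 1.25 allows for baseline being capped at 33/34 while follow-up can reach 40.

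**Formulas.**
- Change score: variance s²(1 + k² − 2rk), 38 df.
- ANCOVA: variance k²s²(1 − r²)(1 + 1/36), 37 df. The last factor is the cost of estimating the slope.
- Half-width: t × √(variance × 2/20), with t = 2.024 (38 df) or 2.026 (37 df).

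Example (s = 5, r = 0.5, k = 1): the change-score variance is 25, so 2.024 × √2.5 = 3.20. The ANCOVA variance is 25 × 0.75 × 1.0278 = 19.27, so 2.026 × √1.927 = 2.81.

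| k | r | Variance ratio, ANCOVA/change | Half-width, SD 5 (change vs ANCOVA) | Half-width, SD 8 (change vs ANCOVA) |
|---|---|---|---|---|
| 1 | 0.5 | 0.771 | 3.20 vs 2.81 | 5.12 vs 4.50 |
| 1 | 0.8 | 0.925 | 2.02 vs 1.95 | 3.24 vs 3.12 |
| 1.25 | 0.5 | 0.918 | 3.7 vs 3.5 | 5.9 vs 5.6 |
| 1.25 | 0.8 | 1.028 | 2.40 vs 2.44 | 3.84 vs 3.90 |

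In the last row the true slope is rk = 0.8 × 1.25 = 1, exactly what the change score assumes. This is ANCOVA's worst case on average: √(1 + 1/36) × 2.026/2.024 ≈ 1.015, a loss of 1.5% of half-width.

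**Simulation check.** With 40,000 normal null trials per cell and k = 1, the half-widths were 3.18 vs 2.80 (SD 5, r 0.5), 2.01 vs 1.94 (SD 5, r 0.8), 5.09 vs 4.47 (SD 8, r 0.5) and 3.22 vs 3.10 (SD 8, r 0.8).

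**Bounded scores.** A second simulation used 40 four-choice items with guessing, integer scores and baseline limited to 6–34 (16 null settings, 20,000 trials each). The variance ratio was 0.83 to 1.02, and the ANCOVA half-width ranged from 0.33 point narrower to 0.04 wider. Null rejection was 4.8–5.2% for the change score and 4.7–5.2% for ANCOVA, so both are valid without normality.

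**Chance imbalance.** The SD of the difference in baseline means is s√(2/20), which is 1.58 (SD 5) or 2.53 (SD 8). A difference above 2 points in either direction therefore occurs in 21% to 43% of trials. With k = 1, a 2-point imbalance shifts the change-score estimate by 2(1 − r), which is 1.0 point at r = 0.5 or 0.4 at r = 0.8. The ANCOVA estimate shifts by about 0.

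**Mixed model.** In a simulated complete two-visit data set with 20 per group, the random-intercept model gave a group-by-time estimate of 2.589 (SE 1.593). The change-score t-test gave the same estimate and SE.

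**The case against.** The strongest case is that this is a preference, not a defect. The change score is unbiased under randomisation, it does use baseline, and UPSIT is a secondary outcome in a pilot sized on feasibility. The gain depends on an SD, a correlation and an SD ratio that the documents do not give. Under bounded scores with the eligibility limits it runs from 17% lower variance to 2% higher, against a minimal important difference of 4 points. All of this stands. It makes the point an optional gain in efficiency, but it does not remove the gain or the small bound on the loss.

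A second objection is that the mixed model equals the t-test only with complete data, while G1 expects 33% dropout and G3 promises intention to treat. Suppose 30 baselines and 20 follow-ups per group, missing at random, with k = 1. Per group, the mixed model's variance is then s²[(1 − r²)/20 + (1 − r)²/30], which is 0.92 (r = 0.5) or 0.97 (r = 0.8) of the change score's 2s²(1 − r)/20. ANCOVA's advantage over it shrinks to about 16% and 4% (half-widths at SD 5: 3.06 vs 2.81 and 1.99 vs 1.95), but it remains. If withdrawn participants' data are left out, as E2 2.h states, the complete-data equivalence holds.

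Third, permuted-block allocation without stratification is perfectly valid. That is so; the remark about matching shows only that chance imbalance is not controlled by design.

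Finally, the documents never name the baseline value. The screening UPSIT is the evident candidate, but the contents of the Week 0 survey are not listed. The fix has to settle this.

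**Conclusion.** The point holds as a free improvement to one secondary outcome. Neither planned UPSIT analysis conditions on baseline, and with complete data the two give the same answer.

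On the assumptions stated above, ANCOVA cuts the variance by 7% to 23% when the SDs are equal at both visits. The half-width then narrows by between about 0.1 point and 0.6 point (5.12 to 4.50 at SD 8, r 0.5). If the follow-up SD is 1.25 times the baseline SD, the reduction is 8% at r 0.5, and at r 0.8 there is a loss of about 1.5% of half-width. The direction is more secure than the size, because the SD and correlation are not in the documents.

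The Fisher's exact analysis of the primary outcome and the sample size of 60 are unaffected.

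**What to change.** In G3:

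- State which UPSIT score is the baseline, and use that same score for the change score and the covariate.
- Make the main UPSIT analysis an ANCOVA of the score at the end of the Fixed-Dose period on group, with baseline UPSIT as covariate. Report the adjusted difference with its 95% CI.
- Keep the t-test or Mann-Whitney U on change as a sensitivity analysis, which also covers non-normality.
- If the mixed model is kept with baseline as a time level, name the group-by-time contrast at the end of the Fixed-Dose period as its test, in place of a promise to explore it. Report the post-taper UPSIT (F4) as a separate contrast.

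The cost is SAP wording and one degree of freedom. ANCOVA uses the same scores and participants as the planned change score and can be fitted in SPSS, the software G3 names.
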